4. INTRODUCTION, BACKGROUND AND SIGNIFICANCE

Background

Chronic kidney disease (CKD) is overwhelmingly prevalent in the United States: more than one in ten American adults are estimated to have CKD and it is the 9th leading cause of death nationally. Kidney failure, or end stage renal disease (ESRD), is the most severe form of CKD, and its incidence is increasing dramatically; the number of Americans with ESRD has tripled in the last twenty years. The incidence of kidney failure is projected to increase even more because of the aging American population. While the yearly incidence rates for ESRD have increased by about 3% for most age groups, the rate for patients over 75 has grown by 10%. The aging American population has substantial implications for the epidemiology of dialysis; by 2050 a quarter of Americans will be 65 or older. The median age at dialysis initiation is 64, and the peak incidence for ESRD is between 80 and 85. For comparison, by 2020 a quarter of the population will be 65 or older and the number of Americans 85 and older will be around twenty million. The incidence of ESRD is also increasing because of the growing prevalence of comorbid and causative conditions such as hypertension and diabetes, particularly in the elderly population.(2-4)

The health care costs associated with ESRD are substantial. In 2012, the Medicare costs for ESRD, excluding medication, accounted for 7.1% of the total CMS budget. (4) The most expensive modality of renal replacement, hemodialysis, is also the most prevalent. In 2015, hemodialysis cost Medicare \$26.7 billion and the expenditure per patient per year was

\$88,195.(5) The estimated cost of dialysis between 2001 and 2010 was approximately \$1.1 trillion.(4)

Hemodialysis access is a conduit through which dialysis machinery may be connected to the patient's circulatory system. The creation and maintenance of access constitutes a significant portion of dialysis costs. A fifth of all ESRD hospitalizations are attributable to access complications. Current clinical practice guidelines maintain that an autogenous arteriovenous (AV) fistula is the ideal vascular access conduit for hemodialysis (Figure 1).(6) Fistulae are superior to prosthetic grafts insofar as they require fewer interventions to maintain patency, have a far lower rate of failure and infection and a longer usable lifespan. Indwelling central venous catheters have the highest risk of death, infection and cardiovascular morbidity.(7) Autogenous AV fistulae confer a mortality benefit when used for dialysis.(1) In the United States, 63% of patients on dialysis use fistulae.(6)

The primary limitation of AV fistulae is the high rate of failure. Between 30%-70% of fistulae suffer primary failure and are never used because they have failed to mature or adapt into suitable dialysis access.(1) This failure nearly always results in a delay in dialysis initiation and requires placement of a dialysis catheter in addition to another surgery for access creation. The financial burden of a failure to mature is accordingly substantial. Dialysis-related expenses incurred by patients in their first year of renal failure are 23% lower if dialysis is started in a mature fistula than without.(8) Techniques to maximize the rates of maturation hold substantial potential for cost savings. Muray-Cases et al. demonstrated that a program of pre-maturation ultrasonography and intervention resulted in a maturation success rate of 78% at the time of dialysis.(9) Notably, the study involved exclusively distal radiocephalic fistulas, a type that has a typical historical rate of maturation failure between 50-70%.(10) Currently, resource limitations enable reimbursed performance of a Duplex ultrasound if maturation is not present at six weeks. Ultrasound surveillance of the maturing fistula in the early postoperative period is not typically performed as CMS and local coverage determination criteria require clinical indications that cannot apply in the early postoperative period. This 'blind period' immediately after fistula creation holds substantial potential for improvement of care.

Research has established that volumetric flow at six weeks after fistula creation correlates with flow at two weeks after creation.(11) This two-week marker has additional and substantial importance; two weeks postoperatively is accepted as the time at which fistula revision can be performed. Most revision surgeries and procedures do not disturb the primary fistula conduit. Taken together, these represent an opportunity to detect and treat maturation failure as early as two weeks postoperatively and enable a fistula to reach maturation by the expected date. Compared to the abovementioned 30-70% failure rate, regular early ultrasound surveillance has resulted in a success rate of 78%. In 2014 alone, such an improvement would result in the salvage of 25,000 – 70,000 fistulas.(12)

A single imaging modality, ultrasonography, is able to assess volumetric flow within a fistula and determine anatomic factors predisposing it to maturation failure or impending late failure. Duplex ultrasound, however, is a resource-intensive practice that requires the dialysis patient to make an additional visit to an outpatient imaging laboratory and requires a trained, formally certified professional ultrasonographer. The examination itself requires 45 minutes to an hour. It

is only complete after image interpretation by a physician which can take an additional 24-48 hours. The substantial commitment of material resources, time, and personnel make formal Duplex ultrasonography too costly for performance of frequent examination, despite the potential for economic and proven clinical and quality improvement that regular scanning holds.(9)

This potential is not theoretical. Doppler ultrasound imaging has demonstrated utility in predicting both fistula maturity and in detecting impending fistula thrombosis.(1, 9, 11, 13-19) Ultrasound criteria for the prediction of maturation failure have been established, and ultrasound can determine the cause of non-maturation and allow planning for surgical intervention.(1) Studies indicate that routine surveillance of fistulae can predict maturation and that a program of routine ultrasound surveillance decreases the rate of maturation failure significantly.(1, 9, 11, 16) A multicenter study of more than 500 upper extremity fistula creations determined that both fistula diameter and volumetric flow at two weeks postoperatively were significant predictors of successful or unsuccessful maturation at six weeks.(11)

While we have described a 50% decrease in maturation failure as reasonable, at least one study of early postoperative ultrasound for maturation monitoring has shown results surpassing this figure. Muray Cases et al. used early ultrasonography to achieve a 78% maturation success rate. In almost all cases of incipient maturation failure, a single, correctible lesion was identified.(9) Remarkably, because of this early detection not a single patient initiated dialysis with a central venous catheter.(9)

Despite the obvious benefit of ultrasonography to reduce maturation failure, regular surveillance imaging of dialysis access is not routinely performed in the United States. Because of the onerous requirements for high trained technical staff, an interpreting physician, a fully equipped and certified vascular laboratory and the time and effort required to undergo formal ultrasound examination, responsible resource utilization precludes frequent formal scanning. In fact, meeting Medicare criteria for medical necessity for such imaging after the maturation study at six weeks requires documentation of quantifiable access malfunction occurring during dialysis or major clinical findings such as massive upper extremity swelling. This limitation is understandable in light of the economic burden associated with a lengthy Duplex examination of hemodialysis access. Ultrasound assessment of dialysis access entails the cost of a dedicated vascular laboratory, an ultrasound apparatus and a qualified ultrasound technologist. A full examination uses color Doppler imaging, pulsed-wave spectral Doppler imaging, and B-mode ultrasound. The patient burden is equally involved, requiring a separate appointment on an additional delay at a vascular laboratory that may be distant from the patient's dialysis center. The study yields a comprehensive assessment of the fistula and the potential to diagnose conditions ranging from aneurysmal degeneration to medial calcinosis and peripheral ischemia.

Ultrasound surveillance does not require such extensive analysis to benefit maturation and thrombosis rates, however. A single variable – volumetric flow – has been shown effective in predicting both maturation and fistula thrombosis.(9, 13, 17-20) The potential for regular ultrasound surveillance to decrease rates of AV fistula maturation failure and thrombosis does not require complete examinations performed by expert ultrasonographers. This study will use a FDA-approved system for rapid ultrasound assessment of fistula flow during existing patient appointments performed by a clinic nurse, requiring minimal training and equipment.

Surveillance using this method, performed by a clinic nurse in the vascular clinic, will enable realization of that benefit in a way that significantly reduces costs and improves patient outcomes.

Device Description

ECHOMARK

The EchoMark is an echogenic polymeric marker used to mark surgical sites with ultrasound. The device has a specially designed form factor that provides [REDACTED] when imaged from different angles and positions. EchoMark is produced with a manufacturing technique that enhances acoustic resonance to maximize brightness under ultrasound. EchoMark is composed of a bioresorbable polymer with a long history of use in sutures and medical devices and dissolves within 18-24 months.

ECHOSURE

EchoSure is an FDA-cleared 3D Doppler ultrasound device that automatically delivers visual and quantitative blood flow information, and may be utilized intraoperatively or postoperatively from the bedside by a nurse or other healthcare provider without the need for special sonographic training.

Benefits

EchoMark and EchoSure together enable the patient care team to collect critical blood flow information intraoperatively and during routine patient examinations postoperatively. The technology displays both a visual indication of arterial and venous blood flow in real-time and provides the quantitative changes in volumetric flow rate in each vessel. This information is critical for:

- Identifying fistulae at risk for maturation failure
- Providing key volumetric flow data to guide appropriate intervention for fistula salvage
- Diagnosing potential issues intraoperatively prior to leaving the OR

5. STUDY OBJECTIVES

Purpose

Stage 1: The primary objective of Stage 1 of the study is to collect data to verify the technology's performance in fistula monitoring. In Stage 1, EchoMark is implanted and monitoring is completed post-operatively. EchoSure data is then captured in an effort to establish normal ranges of the relevant variables in the context of appropriately maturing fistulae and their physiology, which is currently unknown.

Stage 2: The purpose of Stage 2 of the study is to evaluate the performance of the EchoMark and EchoSure (both FDA approved devices) as an ultrasound-based method of monitoring maturation of fistulae. The implant and ultrasound will be used as per IFU. The primary purpose of the study is to collect data on patient outcomes and assess whether or not the information generated from use of

EchoMark and EchoSure can decrease the fistula maturation failure rate and improve the patency of fistulas after up to a year.

Performance Goals

Stage 1:

Primary Performance Endpoint:

- Data collection to verify accuracy
- Data collection to understand the natural history of flow physiology in AV fistulas and classify fistulas that will fail

Primary Safety Endpoint:

- Procedure freedom from Serious Adverse Events (SAEs) during the EchoMark implantation procedure and subsequent post-operative period

Stage 2:

Primary Performance Endpoint:

- Failed fistula maturation rate

Secondary Performance Endpoints:

- Cumulative fistula patency at the end of 1 year
- Volumetric flow data
- Vessel caliber
- Total cost of episode of care

Primary Safety Endpoint:

- Procedure freedom from Serious Adverse Events (SAEs) during the EchoMark implantation procedure and subsequent post-operative care.

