3. STUDY SUMMARY

Title:	Automated Ultrasound Flow Monitoring for Maturation of Peripheral Arteriovenous Fistulae
Protocol Number:	2019-1
Design:	
This is a prospective, single arm, non-randomized, multi-center observational study to demonstrate the performance of the EchoMark and EchoSure devices in patients undergoing peripheral arteriovenous fistula creation for hemodialysis access.
 
Stage 1: EchoMark implantation at the time of fistula creation with scheduled follow up for EchoSure imaging of the fistula maturation process. This stage will produce EchoSure criteria for early prediction of maturation failure.
 
Stage 2: EchoMark implantation and imaging with EchoSure to prove the robustness of the fistula maturation failure criteria established in stage 1 and measure the effect on ultimate fistula maturation rates.

Study Duration:	
Projected enrollment of first patient: May 2020
 
Projected exit of final patient: December 2021

Primary Objective:	
Stage 1: The primary objective of the study is to collect data to verify the technology's performance in monitoring fistula maturation and understand the natural history of AV fistula flow physiology.
 
Stage 2: The primary objective of the study is to assess the ability of the EchoMark and EchoSure system to reduce the rate of failed fistula maturation.

Patient Population:	Patients undergoing upper extremity autologous arteriovenous fistula creation.
Sample Size:	
Stage 1: Up to sixty (60) patients will be enrolled.
 
Stage 2: Up to sixty (60) patients will be enrolled.

Number of Sites:	To be determined
Treatments:	
Stage 1: EchoMark soft tissue marking devices will be placed and monitored using the EchoSure system for 24 weeks or confirmed fistula maturation/failure has been declared by the attending vascular surgeon, whichever comes first.
 
Stage 1: EchoMark soft tissue marking devices will be placed and monitored using the EchoSure system for up to 52 weeks. Upon the decision by the attending surgeon that the fistula failure is confirmed or that monitoring is no longer clinically necessary patients will exit the study

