Endpoints:	
Stage 1:
 
• Data collection to verify accuracy• Data collection to understand the natural history of flow physiology in AV fistulas and classify fistulas that will fail 
Stage 2:
 
Primary Performance Endpoints:
 
• Rate of successful fistula maturation 
Secondary Performance Endpoints:
 
• Cumulative fistula patency at the end of 1 year• Conduit diameter measurements• Volumetric flow measurements
-------------------	--

Inclusion Criteria	
 • Age > 18 years • Patients presenting for upper extremity autologous arteriovenous fistula creation for hemodialysis access where the surgeon selects EchoMark and EchoSure as an appropriate method of monitoring. • Patient is able to sign informed consent and able to participate in all testing associated with this clinical investigation • Women of childbearing potential have a negative pregnancy test.
Exclusion Criteria	
 • Age <18 years old • Patient unable to sign informed consent • Patient participating in another investigational device or pharmacological study • Prisoner or patient from vulnerable populations as defined in 45 CFR 46.
Follow Up:	Patients will have variable follow up depending on the rate of fistula maturation as well as the follow up required by the surgeon per his or her standard practice.

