7. STUDY POPULATION

Number of Patients

Stage 1: Up to sixty (60) patients will be enrolled and both men and women will

be eligible for inclusion. The estimated enrollment period is six months and patients will be followed until the fistula matures and is suitable for use in dialysis or it is ultimately considered non-salvageable by the vascular surgeon.

Stage 2: Up to sixty (60) patients will be enrolled and both men and women will be eligible for inclusion. The estimated enrollment period is twelve months and patients will be followed until then or the decision by the attending surgeon that the fistula failure is confirmed, or that monitoring is no longer clinically necessary patients will exit the study.

Intended Use

The EchoMark and EchoSure devices are intended to be used by a trained medical professional. The EchoMark device is intended to be a Single Use Device, used in a surgical operating suite or equivalent setting. The EchoSure ultrasound devices are reusable and may be used in the operating suite, a post-operative unit such as the ICU or patient floor, or a typical outpatient clinic. When used intraoperatively or in the presence of breached skin, the ultrasound transducer should be used with a sterile probe cover.

Inclusion Criteria

- Age > 18 years
- Patients presenting for upper extremity arteriovenous fistula construction with autologous tissue for the purpose of eventual hemodialysis access where the surgeon has selected EchoMark and EchoSure as the optimal method of vascular monitoring based on clinical assessment and plan
- Patient is able to sign informed consent and able to participate in all testing associated with this clinical investigation
- Women of childbearing potential have a negative pregnancy test

Exclusion Criteria

- Age <18 years old
- Patient unable to sign informed consent
- Patient participating in another investigational device or pharmacological study
- Prisoner or patient from vulnerable populations as defined in 45 CFR 46.

This study will not target the recruitment of any potentially vulnerable subjects. If vulnerable subjects who are educationally or economically impaired present for fistula creation, they will not be given the opportunity to participate in the study.

PATIENT WITHDRAWAL FROM THE STUDY

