10. STUDY PROCEDURES AND METHODS

Patients undergoing fistula creation procedures will be identified. The study will be explained to these patients and informed consent for participation in the study will be obtained from willing patients. A small, FDA-approved tissue marker will be implanted prior to closure of wounds following the Instructions for Use on the FDA-approved labelling.

Stage 1: The fistula will be assessed with intermittent EchoSure examinations, sometimes during routine dialysis visits (maximum 3x/week) to minimize travel. This will conclude when the fistula has entirely matured and the patient begins hemodialysis via the fistula or when the vascular surgeon declares that the fistula has failed despite any and all salvage attempts.

Stage 2: Similar to stage 1 but with implementation of the normative values for relevant variables that resulted from the data collected in stage 1, with subsequent use of the EchoSure flow information in the vascular surgeon's decision making. This stage will also conclude when a year has passed and the fistula is functioning or when the vascular surgeon declares that the fistula has failed despite any and all salvage attempts or that monitoring is no longer clinically necessary.

Actions to Be Taken by Site Staff	Screening and pre-operative evaluation	Clinic Visits	Initiation of dialysis or fistula failure
Consenting	X		
Initial Enrollment Form		X	
Nurse Scan Form		X	
EchoSure Scan		X	
Standard Clinical Exam		X	
End of Trial Period Form			X

11: DATA COLLECTION, ANALYSIS, AND MONITORING

Adverse events are not expected in this study. Unanticipated problems will be reported and discussed with the principal investigator and research coordinator. Patients will be regularly monitored for signs of infection, inflammation or device extrusion. Should the implantable device require removal, it will be removed, and patient will be monitored with conventional methods. The research team will periodically review its protocols to ensure maximal patient safety and data validity.

Source Documentation

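### Stage 2 is meant to assess improved one-year patency, but Stage 1 fistulas that mature or are undecided at exit have no planned one-year status, so Stage 1 gives only a wide bound to compare with

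*Combined protocol and SAP*

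**What the plan says.** All references are to the combined protocol and SAP.

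- **Aim.** Section 5 (Purpose, Stage 2) asks whether the information from EchoMark and EchoSure "can decrease the fistula maturation failure rate and improve the patency of fistulas after up to a year". Sections 3 and 5 list "Cumulative fistula patency at the end of 1 year" as a secondary endpoint, for Stage 2 only.
- **Stage 1 follow-up.** Section 3 (Treatments) has patients "monitored using the EchoSure system for 24 weeks or confirmed fistula maturation/failure has been declared by the attending vascular surgeon, whichever comes first". Section 7 says "patients will be followed until the fistula matures and is suitable for use in dialysis or it is ultimately considered non-salvageable". Section 10 says of the Stage 1 examinations "This will conclude when the fistula has entirely matured and the patient begins hemodialysis via the fistula", or when the surgeon declares failure. Sections 7 and 10 do not repeat the 24-week limit.
- **A second entry labelled Stage 1.** Section 3 (Treatments) has another Stage 1 line in which patients are "monitored using the EchoSure system for up to 52 weeks". It contradicts the line above it and matches the Stage 2 follow-up in section 10: "This stage will also conclude when a year has passed and the fistula is functioning".
- **Comparison.** Section 6 describes a single-arm, non-randomised study. The between-stage test visible in section 8 is a chi-square test on maturation success. Part of the Stage 2 analysis text is redacted.

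**The concern.** An aim to improve something needs a reference value. The only reference inside this study is Stage 1, and its exit rules release a patient when the fistula becomes usable, which is when later loss of patency starts to matter. Nor is an outside reference visible: the failure and success rates quoted in sections 4 and 8 (30-70%, 50-70%, 50%, 78%) all concern maturation, not patency at one year.

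If the plan is followed as written, this part of the Stage 2 purpose will either go unanswered or be answered against a published figure chosen once the Stage 2 result is known. The maturation comparison, on which the sample size rests, is not affected.

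**Working it through.** **1. The plan's own sample size, and what it covers.** Inputs from section 8: 50% v 78% maturation success, alpha 0.05 (taken as two-sided), and the stated beta of 0.8 read as 80% power.

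n per stage = [1.960 × √(2 × 0.64 × 0.36) + 0.842 × √(0.50 × 0.50 + 0.78 × 0.22)]² / 0.28² = (1.330 + 0.546)² / 0.0784 ≈ 45

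45 / (1 − 0.25) = 60. Both stated figures reproduce, with power 80.1% at 45 per stage. The calculation is for maturation only; no one-year patency rate enters it.

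**2. What is known about a Stage 1 fistula at 52 weeks.**

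| State at Stage 1 exit | One-year status under the plan |
|---|---|
| Declared failed | Known, if declared failure is counted as not patent |
| Declared mature | Not planned to be collected |
| Undecided at exit (possible under the 24-week limit) | Not planned to be collected |

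Under the 24-week limit, observation covers at most 24/52 = 46% of the year and stops at least 52 − 24 = 28 weeks short. It stops sooner for a fistula declared mature earlier. Without the limit (sections 7 and 10), slow maturers may be followed longer, but each matured fistula still leaves at maturation or at the start of dialysis through it.

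**3. Bounds on Stage 1 one-year patency.** With n evaluable, m matured and u undecided:

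- lower bound = 0 / n (every matured or undecided fistula is later lost)
- upper bound = (m + u) / n (none is lost)

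Take n = 45, the plan's 50% maturation rate and, as an assumption, u = 0. Then m = 0.50 × 45 = 22.5, that is 22 to 23 fistulas, and the bounds are 0% and about 50%. Any undecided fistula raises the upper bound.

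**4. What a test against the upper bound would need.** As an illustration, let 22/45 be patent in Stage 1 (upper bound) and 32/45 (71%) in Stage 2:

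- pooled proportion = 54/90 = 0.60
- standard error = √(0.60 × 0.40 × 2/45) = 0.103
- z = (0.711 − 0.489) / 0.103 = 2.15, two-sided p = 0.03, uncorrected

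Such a test is possible, but it credits Stage 1 with no loss of patency after maturation.

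**5. Calendar.** May 2020 to December 2021 is 20 months (section 6).

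- Stage 1: six months' enrolment (section 7) ends about October 2020, so the last 52-week status falls about October 2021, inside the window.
- Stage 2: if it follows Stage 1 enrolment, 6 + 12 + 12 = 30 months. Even if it started in May 2020, 12 + 12 = 24 months. Both exceed 20.

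**The case against.** A reader might infer that no Stage 1 patient has any one-year status, so that improvement cannot be assessed at all. The documents do not support that. A fistula declared beyond salvage can be counted as not patent at one year, which at the plan's rate settles about half of Stage 1. Step 4 shows that a high enough Stage 2 rate could exceed the Stage 1 upper bound. What stands is narrower: the comparator is known only within wide bounds, and no test against them is visible in the plan.

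Other points on the plan's side:

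- **One-year patency is only secondary.** True. Section 3 gives failed maturation as the Stage 2 primary objective, and section 6 confines the planned effect calculation to maturation. Even so, section 5 includes improved patency in the study's purpose, so that wording or the data collection has to change.
- **Section 3 contains a 52-week entry labelled Stage 1.** It is probably a mislabel for Stage 2, since it contradicts the line before it and agrees with section 10. It does not rescue the comparison, but the follow-up statements in sections 3, 7 and 10 must be reconciled.
- **Redacted text in section 8 may hold a patency analysis or benchmark.** It may, so I say only that none is visible. An analysis could not replace Stage 1 follow-up that the exit rules do not collect.
- **Stage 2 has gaps too.** It does: patients may leave once the surgeon sees no further clinical need for monitoring, and the calendar is short. A remedy for Stage 1 alone would not be enough.

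**Conclusion.** The concern holds in this form: the plan states an aim of improving patency at up to a year, but collects no later status for Stage 1 fistulas that mature or are undecided at exit. With 45 evaluable patients, a 50% maturation rate, no undecided fistulas, and declared failure counted as not patent, Stage 1 one-year patency is known only to lie between 0% and about 50%. These are logical limits, not likely values; undecided fistulas would widen them.

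Improvement could therefore be tested only against an upper bound that the visible plan does not name, and no one-year benchmark is visible. The change should be made because a stated purpose depends on it, but the powered maturation comparison does not.

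**What to change.** **Preferred.** Record a 52-week fistula status for every patient in both stages, including those who stop scanning early: patent or abandoned with date, interventions, and death or transplant. Use the same chart or telephone method in both stages, so that a difference in ascertainment is not mistaken for a difference in patency. Name the Stage 1 v Stage 2 comparison of one-year cumulative patency as a secondary, non-randomised analysis. Scanning schedules need not change.

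**Cost.** One chart or telephone check per patient (up to 60 + 60 = 120) and a consent line permitting it; no added visit, scan or patient. The Stage 1 checks fit the stated calendar. The Stage 2 calendar must be checked and, on the figures above, probably extended.

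**Alternative.** If later status cannot be collected, reword the Stage 2 purpose in section 5 as describing cumulative patency at one year and drop the claim of improvement. This costs only the stronger claim.

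**In either case.** Reconcile the two Stage 1 entries in section 3, and the 24-week limit there with sections 7 and 10.
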